## Protocol Summary

**Title:** Prehypertension in Haiti

**Study Summary:** We propose an unblinded pilot RCT of 250 persons living with HIV (PLWH), aged 18-65 years, who receive ART care at GHESKIO, are virally suppressed, and have pre-HTN (SBP 120-139 or DBP 80-89 mm Hg) to be randomized to **early HTN treatment** versus **standard of care** (SOC). Participants will be recruited from GHESKIO's HIV clinic. Eligible individuals will complete informed consent and be randomized to early HTN treatment vs. SOC. Participants in early HTN treatment will initiate amlodipine immediately versus those in SOC will initiate amlodipine only if they meet the HTN threshold during the study period. All participants will be followed for 12 months. The primary outcome is mean change in SBP at 12 months between study arms. Secondary outcomes are viral suppression, medication adherence, adverse events, and acceptability. We will also assess CVD risk factors and myocardial/vascular dysfunction among all participants at enrollment.

**Population:** We will recruit 250 PLWH from GHESKIO'S HIV Clinic. Inclusion criteria: PLWH 18-65 years of age, ART duration  $\geq$  1 year , stable regimen  $\geq$  6 months, HIV 1-RNA  $<$  1,000 copies/mL within past 12 months, Pre-HTN (SBP 120-139 or DBP 80-89 mm Hg), no current antihypertensive treatment, receives HIV care at GHESKIO, and willing to provide consent. Exclusion criteria: pregnancy, kidney disease, diabetes, advanced illness with limited life expectancy, plans to move out of the area within the next year, and clinician determination that patient is unstable on ART.

**Number of Sites:** Single site: GHESKIO Center Port au Prince, Haiti

**Study Duration:** 2 years

**Subject Duration:** 12 months

**Primary Aim:** To assess the feasibility of initiating antihypertensive treatment among PLWH with pre-HTN through a pilot randomized controlled trial comparing early HTN treatment to SOC. Feasibility outcomes include enrollment and retention data, proportion who initiate amlodipine, and incremental change in SBP at 12 months between arms. The pilot trial has  $\geq$ 80% power to detect differences in change in SBP  $\geq$  4 mm Hg.

**Secondary Aims:** To also examine the following outcomes and measures:

- a. Viral suppression compared between study arms at 12 months (defined as HIV-1 RNA  $<$  1000 copies/ml)
- b. HIV medication adherence compared between study arms at 6 and 12 months (defined as  $>$ 90% adherence using 3-day pill recalls)
- c. Adverse events compared between study arms at 12 months (defined as Grade III-V adverse events including hypotension, peripheral edema, and other symptoms which may be related to amlodipine)
- d. Acceptability assessed through in-depth interviews with a subset of participants and providers

- e. CVD risk profile measured among all participants at enrollment including obesity, dyslipidemia, diabetes, smoking, physical inactivity, poor diet, and 10-year CVD risk (only among participants  $\geq$  40 years)
- f. Pre-existing myocardial and vascular dysfunction measured among all participants at enrollment using ECG, echocardiography and vascular ultrasound

**Study endpoints and analysis:** The primary endpoint is the difference in mean change in SBP (mm Hg) between study arms at 12 months. Secondary outcomes include viral suppression and medication adherence. We will also measure CVD risk factors among participants. We will compare the mean difference in change in SBP among participants using a linear mixed-effects model (LMM) accounting for repeated measures and correlations within subjects. We will assess incidence of HTN using Kaplan Meier methods. Dichotomized outcomes such as HTN will be analyzed via generalized linear mixed-effects model (GLMM) at all time points and via Fisher's exact test and logistic regression at 12 months. Viral suppression, medication adherence, and CVD risk factors will be compared between study arms using Fisher's exact test. Longitudinal data such as BMI and adherence will be analyzed using LMM and GLMM.

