## 4 STUDY PROTOCOL

### 4.1 Study Objective

We propose a pilot randomized controlled trial to evaluate antihypertensive treatment among PLWH with pre-HTN at GHESKIO. This study will provide critical data on the feasibility, benefits and risks of antihypertensive treatment for CVD prevention among PLWH with pre-HTN that will inform a future definitive trial powered for incident CVD events. For the pilot study, we will enroll 250 PLWH (18-65 years of age) who have been on ART for  $\geq 1$  years with viral suppression within past 12 months and SBP 120-139 or DBP 80-89 mm Hg and no current antihypertensive treatment; randomize them to “early HTN treatment” or the current standard of care (SOC); and follow them for 12 months.

Amlodipine is the recommended first-line anti-hypertensive medication according to Haiti’s new primary care HTN guidelines. Participants in the early HTN treatment arm will initiate amlodipine 5 mg immediately, increasing to 10 mg if SBP  $>130$  mm Hg after 1 month. Participants in the SOC arm will initiate amlodipine only if they develop HTN (SBP  $\geq 140$  or DBP  $\geq 90$  mm Hg). We hypothesize that early HTN treatment will not impact viral suppression and be feasible and safe, with a reduction in BP at 12 months compared to SOC. The primary aim is to assess the feasibility of initiating antihypertensive treatment among PLWH with pre-HTN through a pilot randomized controlled trial comparing early HTN treatment to SOC. Feasibility outcomes include enrollment and retention data, proportion who initiate amlodipine, and incremental change in SBP at 12 months between arms. The secondary aim includes analyzing the following measures: viral suppression, HIV medication adherence, adverse events, acceptability, CVD risk profile, and pre-existing myocardial and vascular dysfunction.

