**Study Outcomes:** The primary quantitative outcome is the difference in mean change in SBP (mm Hg) between study arms at 12 months. Secondary outcomes include **viral suppression** defined per WHO guidelines of HIV-1 RNA <1,000 copies/ml and amlodipine and ART **medication adherence** defined as >90% adherence using 3-day pill recalls, as recommended by the ACTG at enrollment, 3, 6, 9 and 12 months. We will assess for serious **adverse events** including DAIDS Grade III-V symptoms of hypotension, peripheral edema and other symptoms related to medications at every study visit (see Human Subjects). **Feasibility and acceptability** will be assessed by enrollment and retention statistics as well as qualitative in-depth interviews among a subset of 30 participants in the early HTN treatment arm and all study providers at 12 months. We will assess participant attitudes towards the study drug amlodipine. Interviews will explore attitudes about initiating amlodipine, positive/negative effects, satisfaction, intent to continue, home BP measurement, and perceived CVD risk. We will interview providers about implementation challenges and unintended consequences. Interviews will be ~45 minutes, conducted in Creole, audio-recorded, transcribed verbatim, and translated into English for analysis using Atlas-ti. Among all participants, we will measure **CVD risk factors** at enrollment (Table 5). In participants  $\geq 40$  years, we will calculate their 10-year AHA atherosclerotic CVD (ASCVD) risk at enrollment. Pre-existing **myocardial and vascular dysfunction** will be measured at enrollment using ECG, echocardiogram, and vascular ultrasound (Sonosite M-Turbo ultra-sound with P21-x probe). Dysfunction is defined as evidence of left ventricular hypertrophy, diastolic and/or systolic dysfunction, ischemia, increased carotid intima media thickness (surrogate for atherosclerosis), and carotid-femoral pulse wave velocity (measure of arterial stiffness) using imaging criteria from the American and European Societies of Echocardiography and Minnesota criteria. [name] is trained and certified in echocardiography and has experience measuring these parameters with quality assurance from Cornell cardiology in the NHLBI R01 HL143788.

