**Aim 2:** The proportion of participants in each study arm with viral suppression (HIV-1 RNA < 1000 copies/mL) at 12 months will be compared between study arms using the Fisher exact test; we assume participants who are lost to follow-up or dead at 12 months will have HIV-1 RNA > 1000 copies/mL. Other categorical data including medication adherence, CVD risk factors (e.g. diabetes) will be analyzed similarly. Longitudinal data such as BMI and adherence (continuous or binary/categorical) will be analyzed accounting for repeated measures within participants, via LMM and GLMM as described above. We will also consider Generalized estimating equation-based method (so called, marginal or population-averaged model) and will report consistency or meaningful discrepancy. Acceptability will be assessed in qualitative interviews by [name] who is trained in qualitative research using interview information transcribed verbatim, translated into English, and then coded for analysis using a thematic coding scheme. We will also describe adverse events among all participants.

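### Does the adverse-event outcome need one fixed definition and a written between-arm analysis?

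*Combined protocol and SAP*

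**What the plan says.** The Protocol Summary lists the outcome among the secondary ones: "Secondary outcomes are viral suppression, medication adherence, adverse events, and acceptability". Secondary Aims, item c, sets the contrast, "Adverse events compared between study arms at 12 months", and defines the events as "Grade III-V adverse events including hypotension, peripheral edema, and other symptoms which may be related to amlodipine".

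The Study Outcomes paragraph of section 4.7 calls the events serious and describes them as "DAIDS Grade III-V symptoms of hypotension, peripheral edema and other symptoms related to medications at every study visit".

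On analysis, the Summary says "Viral suppression, medication adherence, and CVD risk factors will be compared between study arms using" Fisher's exact test, and adverse events are not in that list. Section 4.9, Aim 2, says of the outcomes handled like viral suppression: "Other categorical data including medication adherence, CVD risk factors (e.g. diabetes) will be analyzed similarly". Its one sentence naming adverse events is "We will also describe adverse events among all participants".

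Safety is part of the trial's hypothesis in section 4.1: "We hypothesize that early HTN treatment will not impact viral suppression and be feasible and safe". Section 4.13 separately requires Grade III-V events and deaths to be reported to the IRBs and the DSMB within 24 hours, with no condition on cause.

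**The concern.** Three things look wrong on a first reading.

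- **Definition.** One text speaks of symptoms that might be due to amlodipine, the other of symptoms due to medications in general. Neither says whether unrelated Grade III-V events count or who judges relatedness. If each case were judged, the judgment would be made with the arm known, because the trial is unblinded and no blinded assessor is described. Standard-of-care (SOC) participants take amlodipine only after developing hypertension, so an event could be called drug-related more readily in the early arm.
- **Analysis.** The Summary promises a comparison, while section 4.9 promises a description. If the description were pooled, it could not speak to safety: 14 of 250 could be 7 versus 7 (difference 0, 95% CI -6.2 to +6.2 points) or 12 versus 2 (8.0 points, 2.3 to 14.5).
- **Schedule.** Sections 3.1, 4.6 and 4.7 assess adverse events at every visit, but the Table 4 row is blank at month 1.

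At stake would be the pilot's safety evidence for the definitive trial it is meant to inform.

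**Working it through.** The plan states no adverse-event rate, sample size or power for this outcome, so there is no figure to reproduce. The check sets the texts side by side, then sizes what can be sized.

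**1. Definition.** Both wordings share Grade III-V severity, and both name hypotension and peripheral edema without any condition on cause. The relatedness wording attaches only to the remaining symptoms. Three readings are possible:

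- the list is open and all Grade III-V events count;
- the phrase describes types of symptom, counted alike in both arms;
- each other symptom is judged case by case.

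The first two contain no arm-dependent filter. Only the third could introduce bias, and only for symptoms other than the two named.

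**2. Comparison or description.** Section 4.9 does not say that the arms are combined. Its adverse-event sentence directly follows the one on acceptability interviews, which section 4.7 limits to 30 early-arm participants and the providers. Reference to all participants therefore reads naturally as scope. The Summary uses the same phrase for the CVD risk profile (item e), and its analysis paragraph still compares CVD risk factors between arms. So the phrase does not exclude a by-arm table, and item c asks for one.

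**3. Method and window.** Having at least one Grade III-V event is a yes/no outcome. The Summary's sentence on dichotomized outcomes gives hypertension only as an example and names Fisher's exact test and logistic regression at 12 months. The categorical-data sentence in Aim 2 is also an open list. The horizon is 12 months, and collection is at every visit. Only a formal start point is unwritten, and randomization is the obvious one.

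**4. Amlodipine exposure.** Inputs: 38% of people with pre-hypertension at ART start developed hypertension within 18 months (section 2.1); 125 per arm (250 at 1:1). Assume that figure applies here and follow-up is complete.

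- Constant hazard: h = -ln(1 - 0.38)/18 = 0.02656 per month. By month 12, 1 - exp(-12h) = 27.3%, or 34 of 125. Mean time on drug is 12 - (1 - exp(-12h))/h = 1.72 months, or 14.4% of follow-up (18.0 of 125 person-years).
- Linear: 0.38 × 12/18 = 25.3%, or 32 of 125. Mean share is 25.3%/2 = 12.7% (15.8 person-years).
- If 12-month incidence were 10% to 40%, the share would be 5.1% to 21.7%.

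This measures the intended contrast between arms. It does not measure an error.

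**5. Cost of an all-cause endpoint.** Newcombe interval for d = p1 - p2, with Wilson limits (l, u): lower = d - √[(p1 - l1)² + (u2 - p2)²], upper = d + √[(u1 - p1)² + (p2 - l2)²].

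- 5 versus 0 of 125: Wilson limits 1.72% to 9.02% and 0 to 2.98%. Lower = 4.0 - √(2.28² + 2.98²) = 0.2; upper = 4.0 + 5.02 = 9.0.
- 10 versus 5 (five unrelated events added to each arm): 4.0 points, -2.2 to 10.5.

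The exact power of a two-sided Fisher test at 0.05 shows the same dilution. The rates are assumptions: 5% and 8.3% borrow the amlodipine discontinuation figures in section 3.1 (5%, and 3.3% + 5% with no overlap), and 1% is assumed for SOC.

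| Related events, early vs SOC | No unrelated events | Plus 10% unrelated in each arm |
|---|---|---|
| 5% vs 1% | 30% | 11% |
| 8.3% vs 1% | 74% | 31% |

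**6. Table 4.** The adverse-event row has 7 marks for 8 follow-up visits. The interview row carries the same marks, although sections 4.7 and 4.10 place interviews at 12 months. Both rows look mis-filled, in a table read from PDF.

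**The case for a change.** The strongest case for a change is that two analysts could build different endpoints from the same data. The trial is unblinded, safety is a stated hypothesis, and a few words would settle the matter.

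Part of this stands. The two definitions do differ, no attribution rule is given, and no sentence in section 4.9 names a by-arm measure for adverse events. The cover from the general sentences is not airtight either: where section 4.9 repeats the dichotomized-outcome sentence under Aim 1, it ties it to blood pressure below 120/80. Section 3.1 also speaks of screening for drug-related events, which sits awkwardly with an all-event count.

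The rest does not carry. Pooling is an inference that item c contradicts. The possible bias is zero under two of the three readings and cannot be sized under the third. The cheap rewrite is also not neutral. Counting every Grade III-V event protects against biased attribution but weakens a drug-specific signal, while counting amlodipine-type symptoms does the reverse. Either is defensible in a pilot of 250, and a report can show both by arm.

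**Conclusion.** No change to the plan follows. This is missing detail that an analyst would fill sensibly: count participants with at least one Grade III-V event by randomized arm through 12 months, show hypotension and edema separately, and add relatedness as a description. Item c points there, and section 4.13 means that recognized Grade III-V events are on record regardless of cause.

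The choice between an all-cause and a drug-related count is a fair trade-off, and the blank month-1 cell is a clerical slip that three text passages override. Whatever definition is used, precision will be modest: 5 versus 5 of 125 gives a difference of 0 with a 95% CI of -5.5 to +5.5 points. The safety result is therefore an estimate and not a powered test.

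The primary SBP comparison is untouched, and section 3.2 bases the post-trial offer of amlodipine on SBP alone. The conclusion assumes that adverse events are asked about alike in both arms at the common visits, as section 4.6 states. The event counts and rates above are illustrative, because the documents give no Grade III-V rate for either arm.

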## 2 BACKGROUND INFORMATION AND SCIENTIFIC RATIONALE

### 2.1 Background Information

Haiti is located on the western third of the island of Hispaniola in the Caribbean Sea and is the poorest country in the Western Hemisphere (Figure 1). Haiti ranks 163 out of 188 countries in the UN Human Development Index, which measures economic, education, and health factors. Haiti has the highest HIV prevalence in the hemisphere (2%); currently an estimated 140,000 adults are living with HIV, with two-thirds of cases in Port-au-Prince. Over the last decade, **CVD surpassed HIV as the leading cause of morbidity and mortality in Haiti.** In 2016, the Global Burden of Disease Project estimated the most common cause of death among adults was CVD (27.2% of deaths) in comparison to HIV (5.6% of deaths). Recent cross-sectional data suggest that 20% of Port-au-Prince residents have HTN (29% age-standardized). Haiti has one of the **highest stroke mortality rates** in the Latin America/Caribbean region, and more than twice that of the neighboring Dominican Republic. One of the strongest stroke risk factors is HTN.

[figure not shown]
Figure 1: Map of Haiti

Cornell-GHESKIO has a **37-year track record** of NIH-supported research in Haiti which has informed WHO and national policies on prevention and treatment guidelines for HIV and associated comorbidities. GHESKIO was founded in 1982 with research evolving from early epidemiologic studies to a major NIH-supported Clinical Trials Unit (CTU) in 2006. This work contributed to the drop in HIV prevalence in the adult population in Haiti, from 6% in 1993 to 2% in 2016, with 60% of those infected on ART. Since 2012, the CTU has **conducted over 20 clinical trials with 98% retention**. GHESKIO is trusted by the Haitian community, the Haitian Government, and international partners. GHESKIO has never closed its clinics in its tenure, even during the 2010 earthquake, cholera epidemic, and periods of political instability.

In 2015, GHESKIO established the Non-communicable Disease (**NCD**) **Research Unit**, led by the PI of this proposal, to evaluate CVD among HIV patients and the general population. With NIH support (D42TW0009606-S1), we conducted the first population-based survey of HTN in the slums of Port-au-Prince and found that 12% of 18-30 year-olds had HTN not accompanied by risk factors such as obesity, smoking, and diabetes; this prevalence is ~3 fold higher than similarly aged Black Americans. In 2018, we received funding (R01 HL143788 2018-2023; [name], PI) to establish the **country's first longitudinal cohort to evaluate the epidemiology of HTN** including CVD risk factors (e.g. diabetes, kidney disease, HIV, diet, inflammation), diseases (stroke, myocardial infarction, heart failure, and cardiac death), and poverty-related social determinants. This study dramatically increased our capacity to conduct CVD trials through assessment of CVD risk factors, training in ECG and echocardiography, validation of community-based BP measurement, and formation of a CVD adjudication committee. In 2019, the PI of this proposal led a collaboration with the Ministry of Health and international experts to develop Haiti's first **national primary care HTN guidelines** based on WHO recommended algorithms.  **Amlodipine**, was selected for its safety, the lack of laboratory monitoring, and its effectiveness in Blacks. We have also received funding (RESOLVE to SAVE LIVES, PI [name]) for HTN medications and support for guideline implementation.

**HTN in PLWH is associated with mortality:** Cornell-GHESKIO's CVD research began with the evaluation of CVD outcomes among PLWH who had been followed for 10 years (the *GHESKIO ART Cohort*). This cohort includes 816 HIV-infected adults who started ART in 2005-2008 when ART first became widely available in Haiti. At ART initiation, their median age was 39 years (IQR 33-46), 58% were female, and their median CD4 count was 281 cells/mm^3 (IQR 250-311). At ART initiation, 5.3% had HTN. In multivariable analysis, HTN at ART initiation independently predicted mortality during 10 years of follow-up (HR 2.47 [95% CI 1.10-5.57] after adjusting for age, sex, and CD4 count at ART start). Figure 2 shows Kaplan Meier survival curves of those with normal BP and those with HTN at ART initiation. One-third of the deaths among those with HTN were from stroke. Over the median follow-up of 7.3 years, HTN prevalence increased to 43% (HTN incidence 34/1000 person-years). HTN prevalence did not differ by gender and was 18% in patients <40 years, 37% in 40-59 years, and 60% in ≥60 years. Incident HTN was strongly predictive of death.

**Figure 2: Survival of HIV-infected adults with and without HTN at ART initiation**

We analyzed a more recent cohort of 762 PLWH who initiated ART between 2013-2015 at GHESKIO and found HTN prevalence at time of ART initiation doubled to 12% and HTN incidence tripled to 108/1000 person-years (Table 1). Of note, 38% of PLWH with pre-HTN at time of ART start developed incident HTN within 18 months. We postulate that the GHESKIO ART Cohort had a higher number of persons with AIDS at ART start as compared to this later cohort.

### Pre-HTN is associated with increased CVD risk in

#### PLWH as compared to adults without HIV:

A study from the US quantified the increased CVD risk among PLWH with pre-HTN as compared to pre-HTN adults without HIV. PLWH with pre-HTN had increased risk of myocardial infarction (adjusted HR 1.8 [95% CI 1.22-2.68]). Our preliminary data show that 27% of PLWH with pre-HTN compared to 7% of HIV-uninfected adults with pre-HTN had elevated 10-year CVD risk, a >3-fold higher prevalence (Figure 3). We used the AHA Pooled Cohort Risk Equations to estimate 10-year CVD risk among adults 40-79 years. Elevated 10-year risk is defined as a predicted risk of  $\geq 7.5\%$  or having diabetes. We included 192 PLWH (median age 45, 72% female, median duration of ART 3 years) and 153 adults without HIV (median age 41 years, 61% female). The relative contributions of specific risk factors explaining this increase among PLWH need further investigation.

## 2.2 Scientific Rationale

[figure not shown]
HIV-associated CVD has tripled over the past two decades globally and HTN is a major driver of CVD among PLWH. Around the globe, >35% of PLWH have HTN, and >50% of PLWH >50 years of age have HTN. In addition to traditional CVD risk factors, the pathophysiologic mechanisms leading to HTN among PLWH may include virologic and treatment-related factors influencing inflammation, immune mediation, lipodystrophy and the renin-angiotensin-aldosterone system.

